We will leverage two ongoing dissemination initiatives to support our recruitment goals: Project BEST (Bringing Evidence-Supported Treatment to South Carolina), a statewide dissemination initiative funded since 2007 by The Duke Endowment; and the Program on Adolescent Traumatic Stress (PATS), a regional initiative funded by SAMHSA since 2011. Together, as of June 2016, 30 learning collaboratives have been completed via Projects BEST and PATS with 799 clinicians (over 600 of whom are study eligible), 166 senior leaders, and > 3,500 child training cases. Drs. [name] and [name] (Co-Is) co-lead these projects and fostered the agency partnerships that will support the proposed effectiveness-implementation trial (see letters of support), including 4 sites that served as partners in our R34. Projects BEST and PATS are not explicitly linked to the study except that they will establish the population of eligible providers from which we will recruit. Each dissemination initiative maintains a roster of providers who completed TF-CBT training within the past 10 (BEST) or 5 (PATS) years. We will use this combined roster of over 600 study-eligible providers to identify candidates for recruitment (see Milestones).

Notably, Projects BEST and PATS offer training agency-wide, not through a selective or competitive process. More than two-thirds of providers in these agencies (~70%) complete the training, resulting in an externally valid sample of providers that is diverse with respect to years of experience, race/ethnicity, and other key variables. The learning collaborative process is comparable to that of other regional or national dissemination initiatives community-based providers may encounter.⁷⁹⁻⁸¹ **Recency of training is also highly variable. Only 109 of 602 rostered study-eligible providers (18.1%) completed their training within the past year.** This ensures that our sample will be diverse with respect to training recency. Finally, even among recently trained providers, we have found that knowledge and skill is highly variable. For example, we found mean post-training TF-CBT Knowledge scores of 61% in a survey of 39 providers who recently completed training via PATS.⁸²

C2. NIMH R34 Phase 1: Semi-Structured Interviews with TF-CBT Certified National Trainers.

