D4b. Study Design. The trial will randomize to tablet-facilitated vs. standard TF-CBT 400 providers recruited from partnering agencies. We will stagger recruitment of providers to ensure an effective balance in level of coordination across clinics, providers, and patient assessments. We will recruit from clinics in the United States (~400 providers). In our pilot R34, 13 of 17 providers (76.5%) invited to participate in the study completed treatment with at least one study case. Applying this percentage to our proposed sample of 400 providers, we will need to invite roughly 520 providers to participate in the current trial. Collectively, this represents only about 25% of the total number of providers at these partnering clinics who will meet eligibility criteria for the study.

All study assessments with provider participants and family participants (i.e., baseline and 3-, 6-, 9-, and 12-month post-baseline assessments) will be conducted by independent, trained study evaluators blind to treatment condition and study hypotheses (Aim 2); whereas qualitative interviews will be conducted by the project coordinator (Aim 4). Baseline assessments will be coordinated with partnering clinics and completed via televideo. We will provide an iPad to each clinic for baseline telehealth assessments, which will be conducted using a secure, IRB-approved teleconsent platform (doxy.me). Post-baseline assessments and audiorecorded qualitative interviews will be completed by telephone by independent trained study staff. Measures were chosen based on strong psychometric support as well as their ease of telephone administration. Completion of assessments in person would have been impractical and cost prohibitive (i.e., would require numerous subawards and training, oversight, and coordination of many evaluators who are willing to travel extensively and flexibly with only partial support). Semi-structured interviews will be conducted as families complete treatment (n ~ 20) and at study completion with diverse samples of ~25 providers (including ≥ 10 who opt out of the tablet condition or had low tablet use), ~10 supervisors, and ~10 senior leaders (i.e., agency directors, program managers) to assess barriers and facilitators associated with implementing and sustaining tablet-based resources. These interviews will be completed over the telephone or using a videoconferencing program (like Facetime) called Doxy.me.

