D4c. Recruitment of Providers. 400 providers will be recruited from partnering mental health service settings to participate in this study. Providers will be identified for recruitment from the roster of providers who have been trained in TF-CBT within the past 10 years through our BEST and PATS projects. See letters of support for a letter of commitment from South Carolina Department of Mental Health (covering 17 SC DMH centers) as well as letters from several SC-area child advocacy centers and partnering agencies nationwide. These sites collectively have significant geographic (i.e., rural/urban) and racial/ethnic diversity. This roster is maintained by Drs. [name] and [name] (Co-Is). **Inclusion criteria** are as follows. Providers must be full- or part-time employees of the partnering clinic and must have obtained at least a Master's degree in social work, counseling, clinical psychology, or related field. Each provider will be asked to refer 4-5 cases to the study to maximize likelihood that treatment is completed with at least 3 study cases. Although incentives cannot be given to providers due to state regulations, we propose as an alternative incentive that partnering clinics may keep study iPads for use by their providers upon completion of the study.

D4d. Randomization of Providers. Providers will be randomly assigned to the tablet-facilitated TF-CBT vs. standard TF-CBT condition. Providers will be blind to condition until their initial study-eligible family has been enrolled in the study under their care. Providers assigned to the tablet TF-CBT condition will be assigned a unique access code to enable tracking of the frequency and usage of each component of the tablet toolkit.

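### D4b's 520 invitations cannot be about 25% of the eligible pool the protocol counts: on the 602-provider roster they are about 86%, and 25% fits a 120-provider target

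*Protocol*

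**What the plan says.** Protocol D4b sets the target: "The trial will randomize to tablet-facilitated vs. standard TF-CBT 400 providers recruited from partnering agencies". It takes the yield from the pilot, where "13 of 17 providers (76.5%) invited to participate in the study completed treatment with at least one study case", and concludes that "we will need to invite roughly 520 providers to participate in the current trial". It then puts that number in proportion: "Collectively, this represents only about 25% of the total number of providers at these partnering clinics who will meet eligibility criteria for the study".

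Other sections identify the pool. C1 says "We will use this combined roster of over 600 study-eligible providers to identify candidates for recruitment" and gives the count: "Only 109 of 602 rostered study-eligible providers (18.1%) completed their training within the past year". D4c repeats the source: "Providers will be identified for recruitment from the roster of providers who have been trained in TF-CBT within the past 10 years" through the two initiatives. Section E, under Provider Recruitment, again names a roster of over 600, calls it growing, and treats past training through the two initiatives as the evidence that a provider is qualified. C1 also reports 799 clinicians trained as of June 2016 and states that "More than two-thirds of providers in these agencies (~70%) complete the training".

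The provider target itself varies:
- 400 in D4b, D4c and D8h
- 60 + 60 in D1
- 250 in Section E
- at least 120 in SAP 2.9.1

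The child target is 360 throughout, with three cases per provider.

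**The concern.** The numerator and the percentage in D4b do not belong together. If 520 people are to be invited from a roster of about 602, nearly the whole roster is used, whereas the sentence tells the reader that about three quarters of the eligible pool stays in hand. The figure matters because D8h says the initial sample size was determined by how many providers and children could feasibly be recruited from the partners. A reader judging whether 400 providers is realistic would rely on this sentence and be misled about the margin. The mismatch also suggests that the provider number was changed in some places and not in others.

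**Working it through.** **Inputs.** Target 400 and pilot rate 13/17 = 76.5% (D4b). Eligible roster 602, all trained clinicians 799, and about 70% of agency providers completing training (C1). Alternative targets: 60 + 60 = 120 (D1), 250 (Section E), at least 120 (SAP 2.9.1). Detectable effects: 0.34 SD printed beside 400 providers, and 0.5 SD with 60 providers (D8h).

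**1. Reproduce the invitation count.** Invitations = target / rate = 400 / (13/17) = 523. D4b's rounded 520 is confirmed.

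**2. Share of the counted pool.** 520 / 602 = 86.4% (unrounded, 523 / 602 = 86.9%). The stated 25% is not reproduced.

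**3. Wider denominators.**
- All trained clinicians, eligible or not: 520 / 799 = 65%.
- Every provider in the agencies, trained or not. The 70% is the share who complete training, so the trained count is the one to scale up: 799 / 0.70 = 1,141, and 520 / 1,141 = 46%.
- Pool needed for 25%: 520 / 0.25 = 2,080, about 3.5 times 602. No section gives a number near this.

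**4. Which target the 25% fits on the roster of 602.**

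| Target | Invitations at 13/17 | Share of 602 |
|---|---|---|
| 120 | 157 | 26% |
| 250 | 327 | 54% |
| 400 | 523 | 87% |

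Only 120 gives a figure that rounds sensibly to about 25%. It also agrees with 360 / 3 = 120. The 250 target comes near only on the 1,141 denominator (327 / 1,141 = 29%), which counts untrained and ineligible providers.

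**5. Reserve if 400 is kept.** Uninvited: 602 - 520 = 82, or 14% of the roster. Expected yield if the whole roster is invited: 602 x 13/17 = 460, or 60 above target. Lowest workable rate: 400 / 602 = 66%. The pilot's 13 of 17 has an exact 95% interval of about 50% to 93%, so 66% lies inside its uncertainty.

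**6. Check on power.** Scaling D8h's own 60 providers for 0.5 SD by 1/sqrt(n), 0.34 SD needs 60 x (0.5/0.34)^2 = 130 providers. At 120 the detectable effect is 0.5 x sqrt(60/120) = 0.35. At 400 it would be 0.5 x sqrt(60/400) = 0.19. The printed 0.34 therefore belongs to roughly 120 to 130 providers.

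**The case against.** The strongest reply is that D4b's denominator is not the roster. It speaks of providers at the partnering clinics who will meet the criteria. The inclusion list in Section E asks only for training in TF-CBT, and Section E says most providers at these clinics qualify. The 602 appears in an account dated June 2016, the roster is called growing, and the protocol is dated March 2022. This stands in part: 602 should not be treated as the true current figure, and 86% is the share of the documented roster only. But C1, D4c and Section E all tie recruitment to BEST/PATS trainees, no later count is given, and the pool would have to more than triple.

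A second reply is that the sentence is only a symptom of the unreconciled provider number, and that 25% is about right for the 120-provider design the SAP describes. That also stands, and it determines the order of the fix. It does not rescue the sentence as written, because 520 and 25% cannot both hold against the documented roster.

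A third concerns the yield. In the pilot all 17 invited providers consented, so 76.5% is active participation, not acceptance. Two of the four who did not take part had no suitable case within a four-month window. D1 randomizes providers when their first study patient is consented, so a rate defined by at least one case suits a count of randomized providers. This is accepted: the pilot rate is a fair basis, though imprecise with 17 providers.

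A reader might go further and infer that a shortfall below 400 would breach the power statement. The documents do not support that, because D8h's own figures place 0.34 SD at roughly 120 to 130 providers.

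**Conclusion.** The contradiction holds. On the only eligible pool the documents count, about 520 invitations are 86%, not 25%, and the most generous documented denominator gives 46%. The stated share is consistent with a 120-provider target (26%). That the 25% was carried over from such a plan is an inference, although D1, the child target and the SAP all point to 120.

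A reader might conclude that no recruitment reserve exists at 400. That is too strong. About 82 rostered providers would remain uninvited, and inviting everyone would be expected to yield about 460. What is missing is the reserve of roughly 75% that D4b implies. At 400 the margin is thin, and it disappears if active participation falls below 66%.

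These results assume that 602 is the pool and that the pilot rate carries over. A larger current roster would reduce the share in proportion. This is a feasibility statement to correct. It changes no eligibility rule, randomization step, outcome or analysis.

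**What to change.** First reconcile the provider target across Protocol D1, D4b, D4c, D8h and Section E and SAP 2.9.1, choosing among 400, 250, 60 + 60 and at least 120. Then restate in D4b, for the target that is kept, the invitation count and its share of the current roster, with the date of that count. If 120 is kept, the 25% can stay in substance, and the 400 and 520 are the figures to change. If 400 is kept, also state the minimum active-participation rate at which it remains reachable (66% on a roster of 602, recalculated for the current count) and track observed participation against it.

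The cost is a few sentences and one roster count, plus a simple tracking figure if 400 is kept. The downside is a less favourable feasibility figure in that case.

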All mental health treatment sessions will be videorecorded and coded for fidelity and engagement by coders blind to study purpose and hypotheses. Videorecording of sessions is standard and typical in clinical practice for trainers or supervisors to review session recordings; in fact, most of the providers on the roster of eligible providers for this study recorded sessions while receiving training and ongoing consultation in TF-CBT.

Providers will be randomly assigned to treatment condition (tablet-facilitated vs. standard TF-CBT). Providers assigned to the tablet condition will be provided a unique study id to minimize risk of contamination. The tablet TF-CBT platform will not be accessible without a study-assigned userid. Eligible providers will have been fully trained in TF-CBT via ongoing dissemination initiatives independent of this study and will carry active child trauma cases. Each provider will treat three families during the course of the trial. We chose to recruit 400 providers and 3 families per provider, instead of fewer providers with more families per provider (e.g., 70 and 5), to minimize threats associated with provider turnover and variable patient caseloads. Providers will not be informed of their condition until their initial study-eligible family has been enrolled under their care. Although we discussed the possibility of integrating a tablet-based resource into the control condition to facilitate patient blinding, our agency partners were not receptive to this.

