D8a. Hypothesis 1: Higher levels of provider fidelity will be observed in tablet-facilitated vs. standard TF-CBT. To determine if the target of **provider fidelity** was affected by access to the tablet and tablet use, a 2-level MLM (level-1 child; level-2 provider) will be used. Fidelity will be measured by the TF CBT TPOCS-S. Fidelity scores will be calculated per child participant such that each provider will have 3 ratings. An aggregate score for the entire treatment of a case is consistent with prior use of these fidelity measures.¹³² An aggregate fidelity score will allow the hypothesis of differences across condition to be tested while accounting for nesting of multiple cases per provider. Similarly, this measurement lends itself to use as a mechanism of treatment response (Hypothesis 5). The level-1 model will include a fixed effect corresponding to the mean participant fidelity score with a random effect corresponding to variability across participants. The level-2 model will include a dichotomous fixed effect representing the condition to which each participant will be randomized (tablet-facilitated vs. standard TF-CBT). The inclusion of additional child (level-1) and provider (level-2) covariates will be evaluated by estimating changes in model fit according to the deviance statistic for nested models and the AIC/BIC for non-nested models.¹³⁰ Case order (1st-3rd) will be included as a level-1 fixed effect to examine the potential increase in fidelity across cases due to practice effects.

D8b. Hypothesis 2: Greater child engagement will be observed in tablet-facilitated vs. standard TF-CBT. A 2-level MLM (level-1 child; level-2 provider) will evaluate the effect of access to the tablet and tablet use on the target of **child engagement**. An aggregate CIRS score for each child will be used for the reasons described in Hypothesis 1. A prototypical level-1 model will include a fixed effect representing engagement scores for children at level 1. The level-2 model will include a dichotomous fixed effect representing the condition to which each child was randomized (tablet-facilitated vs. standard TF-CBT). The inclusion of additional child (level-1) and provider (level-2) covariates will be evaluated by estimating changes in model fit according to the deviance statistic for nested models and the AIC/BIC for non-nested models.¹³⁰ Case order (1st-3rd) will be included as a level-1 fixed effect to

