examine the potential increase in engagement across cases due to practice.

D8c. Hypothesis 3: Greater improvement in clinical outcomes will be observed at post-baseline assessments among children receiving tablet-facilitated TF-CBT vs. standard TF-CBT. Response to the intervention will be evaluated with a piecewise longitudinal MLM that contains 3 levels. Level-1 will correspond to measurement period, level-2 to child, and level-3 to provider. The primary outcome for Hypothesis 3 will be scores on the K-SADS-PL, UCLA PTSD Index, CDI, and CBCL. A piecewise model allows for separate change trajectories to be estimated for distinct periods of time. Patients are expected to show more rapid change during treatment than during follow-up (roughly corresponding to 9- and 12-month post-baseline period). The level-1 model will include a fixed effect for pretreatment (intercept), rate of change during treatment, and rate of change for the follow-up period. Time varying covariates (level-1) will be added to the model based on a theoretical rationale and changes in model fit. The level-2 model will account for child level covariates, including comorbid symptoms and trauma history. The level-3 model will include a dichotomous fixed effect representing the condition to which each provider was randomized (tablet-facilitated vs. standard TF-CBT). Of interest is the cross-level interaction between rate of change during treatment and the condition to which the provider was assigned. Cross-level interactions between the rate of change during follow-up also will be examined.

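### Families referred after a provider learns the arm may differ between arms, so the fidelity and engagement models should fix their baseline covariates in advance and the provider counts should be reconciled

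*Protocol*

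**What the plan says.** **Allocation and disclosure.** Providers are randomised when their first study patient consents (protocol D1). D4b adds: "Providers will not be informed of their condition until their initial study-eligible family has been enrolled under their care". D4d repeats this, and section E.1.a puts randomisation directly after that enrolment. D1 and D4c expect four to five referrals per provider, so that three cases complete treatment.

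**Referral safeguards.** Under B4, providers refer only patients already judged to be receiving TF-CBT; E.2.a sets the looser bar of a possible candidate. Under E.1.a, clinics introduce the study, the study team decides eligibility, and a blinded evaluator handles consent and assessment.

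**Hypotheses 1 and 2.** D8a and D8b fix two terms. The first is condition, which D8b describes as a "fixed effect representing the condition to which each child was randomized", although D8c and the design make the provider the randomised unit. The second is order: "Case order (1st-3rd) will be included as a level-1 fixed effect". For everything else, "The inclusion of additional child (level-1) and provider (level-2) covariates will be evaluated by estimating changes in model fit", using deviance for nested models and AIC/BIC for non-nested ones. D8a adds: "Fidelity scores will be calculated per child participant such that each provider will have 3 ratings".

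**Hypothesis 3.** Here the protocol does name child covariates: "The level-2 model will account for child level covariates, including comorbid symptoms and trauma history".

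**Who is analysed.** D4b says: "All mental health treatment sessions will be videorecorded and coded for fidelity and engagement". D8g analyses all eligible, enrolled cases.

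**SAP 2.9.1.** It does not carry the all-enrolled rule. It names no covariate and no case-order term for fidelity or engagement.

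**Counts.** Providers number 60 vs 60 (D1), 400 (elsewhere in D1, D4 and D8), 250 (E.1.a) and at least 120 (SAP). The child target is 360.

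**The concern.** Provider randomisation balances providers. It balances the children too only if the choice of children does not depend on the arm. Once a provider knows whether the toolkit is available, the choice of the next family to put forward can depend on it. A provider with the toolkit might, for example, put forward younger or harder-to-engage children. The safeguards act on eligibility, consent and assessment, which come after referral, so they limit this risk without removing it.

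Fidelity and engagement are the trial's targets and the mediators in Hypotheses 4 and 5. A difference in case mix between arms could be read as a toolkit effect, could hide one, and would carry into the mediation paths.

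The analysis should answer with baseline covariates fixed in advance. A fit criterion measures association with the outcome, not imbalance by arm. With no candidate list, the model on which Hypotheses 1 and 2 are tested is also not settled until the data are seen.

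**Working it through.** **1. The plan's own figure (D8h).** Inputs: alpha 0.05 (two-sided assumed), power 0.80, ICC 0.15, equal arms, stated detectable effect 0.34 SD with 400 providers.

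Detectable effect = k x sqrt[(4/N) x (1 + (m - 1) x ICC)], with k = 1.960 + 0.842 = 2.802, m children per provider and N children in all.

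| Providers x children | N | Detectable effect (SD) |
|---|---|---|
| 120 x 3 | 360 | 2.802 x sqrt(4/360 x 1.30) = 0.337 |
| 250 x 3 | 750 | 2.802 x sqrt(4/750 x 1.30) = 0.233 |
| 400 x 3 | 1,200 | 2.802 x sqrt(4/1200 x 1.30) = 0.184 |

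Only 120 x 3 gives 360 children, and only it reproduces 0.34.

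**2. Share of children who may be referred with the arm known.** Assume every provider enrols at least one family.
- 120 providers, 360 children: (360 - 120)/360 = 67%.
- 250 providers, 360 children: (360 - 250)/360 = 31%.
- 400 providers, 360 children: 0.9 children per provider, so no share can be computed.

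These are upper limits, because a second family referred before the first is enrolled would still be masked.

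**3. What a shift would do (illustration; the shift is assumed).** Suppose later children differ between arms by 0.1 to 0.3 SD in the outcome they would have had anyway. The contrast moves by share x shift.
- 120 x 3: 0.667 x 0.1 to 0.3 = 0.07 to 0.20 SD, against a detectable 0.34.
- 250 providers, 360 children (m = 1.44): 0.306 x 0.1 to 0.3 = 0.03 to 0.09 SD, against 2.802 x sqrt(4/360 x 1.066) = 0.305.

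Fidelity is a provider behaviour, so a child-mix shift would pass through only in part.

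**4. Does case order correct it?** No. Order is balanced across arms, so its main effect carries no information on an arm difference within later cases. A simulation of 150 trials (120 x 3, ICC 0.15) shifted a baseline variable by 0.4 SD in the tablet arm's second and third cases, with a coefficient of 0.5 on the outcome. The expected bias is 0.667 x 0.4 x 0.5 = 0.133 SD. The observed bias was 0.138 SD both with and without case order, and 0.007 SD once the baseline variable was included.

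**5. What the fit rule itself costs.** Take one covariate correlated r with the outcome and imbalanced by an assumed 0.3 SD in later families. A 0.05 deviance test (3.84 on 1 df) has noncentrality 360 x r^2/(1 - r^2). Bias if omitted = r x 0.3 x 0.667. Expected bias = that x probability of omission.

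| r | Probability omitted | Bias if omitted (SD) | Expected bias (SD) |
|---|---|---|---|
| 0.10 | 0.52 | 0.020 | 0.010 |
| 0.15 | 0.18 | 0.030 | 0.005 |
| 0.20 | 0.03 | 0.040 | 0.001 |

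The maximum is about 0.011 SD, near r = 0.08 to 0.09. The noncentrality treats the children as independent. A simulation with ICC 0.15 and r = 0.10 (4,000 runs) gave omission 0.51 and bias 0.019 SD when never adjusted.

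**6. First families only.** These are referred before disclosure. Detectable effect = 2.802 x sqrt(2/n per arm):
- 60 vs 60: 0.51 SD.
- 48 vs 48 (20% provider dropout, D8h): 0.57 SD.
- 125 vs 125: 0.35 SD.

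**The case against.** **The harm and the remedy are only loosely connected.** This stands. A measured covariate strong enough to move the contrast much would almost never be dropped by a deviance test at 360 children. An unmeasured difference would survive a fixed covariate list as well. A reader might infer that the fit rule costs the 0.07 to 0.20 SD of step 3. It does not: step 5 puts its expected cost at about 0.01 SD. What the remedy gives is a model settled in advance and adjustment for measured case mix.

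**Not every later family is unmasked.** This also stands. A reader might infer that all families after the first are referred with the arm known. The documents tie disclosure to enrolment of the first family, so an overlapping referral would be masked. In the pilot (C5), 24 families were referred within two months, so overlap is plausible.

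**Three ratings and four to five referrals need not conflict.** Largely right. D1 and D4c present the extra referrals as an allowance to reach three completed cases, and no passage says that only completers are rated. A reader might also infer more than three enrolled families per provider and so a larger unmasked share. At the pilot's 87.1% enrolment, four referrals from each of 120 providers would give about 418 children, above the stated target of 360.

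**The SAP is not silent on model building.** It refers to the Singer and Willett guidelines, which the protocol also cites for its fit criteria. The SAP may therefore intend the same rule. That leaves the covariates just as open.

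**Conclusion.** The point holds as a recommendation of moderate weight. The documents establish that providers continue to refer after learning their arm, that this may affect up to 67% of children at 120 x 3 (31% with 250 providers and 360 children), and that the models for the two targets commit to no baseline covariate. They do not show that referrals differ between arms; the size and direction of any difference are unknown, and every shift used above is an assumption. The direct cost of choosing covariates by fit is small, about 0.01 SD for one covariate imbalanced by 0.3 SD. Unmeasured selection would remain under any covariate set.

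The conflict in provider counts is firmer, because it rests on the documents' own arithmetic: 400 x 3 is 1,200, not 360, and 0.34 SD does not reproduce with 400 providers. It also matters here, because the share of children exposed to unmasked referral cannot be settled until the count is.

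**What to change.** 1. In D8a, D8b and the SAP, replace fit-based selection for Hypotheses 1 and 2 with a fixed set of baseline variables already collected, for example child age, baseline child CATS (trauma screen) score and trauma history. State that this adjusts only for measured case mix.
2. Keep case order, defined as enrolment order, for all enrolled children with recordings. Reword the three ratings and the first-to-third ordering to match, and add the term to the SAP.
3. Carry the D8g all-enrolled rule into the SAP.
4. Report baseline characteristics of first and later families by arm. A first-family-only analysis is optional and descriptive: it detects only about 0.51 SD at 60 vs 60, and a first-versus-later contrast cannot separate referral selection from the practice effects that D8a and D8b anticipate.
5. Name the provider as the randomised unit in D8a and D8b, as D8c does.
6. Reconcile the provider counts (60 vs 60, 250, 400, at least 120) with 360 children, and restate the detectable effect for the count that applies.

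The cost is wording in the protocol and SAP, one baseline table and, if wanted, one descriptive analysis. No new data or session coding is needed: the youth CATS in D4j already records trauma exposure and PTSD symptoms at baseline.
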